6.4.3.1 Pharmacodynamic

The respiratory parameters will be descriptively summarized by treatment and listed by individual at each time point by treatment and visit for each of the cohorts using descriptive statistics. These will also be supported with graphical displays in order to ease making comparisons.

6.4.3.2 Pharmacokinetic

All pharmacokinetic parameters will be descriptively summarized by treatment and listed by individual at each scheduled time point for each of the cohorts. AZD6140 and AR-C124910XX plasma concentrations will be summarized by treatment, reported as descriptive statistics and listed by individual at each scheduled time point for each of the cohorts.

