Clinical Pharmacology Study Protocol

[figure not shown]
Drug Substance AZD6140
Study Code D5130C00028
Edition Number 1.0
Date

An Exploratory, Double-Blind, Randomized, Placebo-Controlled, 2-Period Crossover, 3 Cohort Pharmacokinetic/Pharmacodynamic, Single Center Study to Assess the Effect of AZD6140 on Respiratory Parameters in Healthy Subjects, Mild Asthmatics and COPD Patients Age 55 to 75 Years

The following Amendment(s) and Administrative Changes have been made to this protocol since the date of preparation:

Amendment No.	Date of Amendment
_____	_____
_____	_____

Administrative change No.	Date of Administrative Change
_____	_____
_____	_____

ASTRAZENECA PROCEDURES IN CASE OF EMERGENCY

In the case of a medical emergency you may contact the Clinical Study Team Leader. If the Clinical Study Team Leader is not available, contact the Clinical Study Team Physician at the AstraZeneca Research and Development site shown below.

Role in the study	Name	Address and Telephone number
Clinical Study Team Leader		
Clinical Study Team Physician		

For further clarifications regarding:

- Procedures in case of medical emergency see Section 8.2
- Procedures in case of overdose see Section 8.3.
- Procedures in case of pregnancy see Section 8.4 (not applicable)

PROTOCOL SYNOPSIS

An Exploratory, Double Blind, Randomized, Placebo-Controlled, 2-Period Crossover, 3 Cohort Pharmacokinetic/Pharmacodynamic, Single Center Study to Assess the Effect of AZD6140 on Respiratory Parameters in Healthy Subjects, Mild Asthmatics and COPD Patients Age 55 to 75 Years

Investigator

6

Study centre(s), type and number of subjects planned

Approximately 24 subjects (male or female of non-child bearing potential) including 8 healthy volunteers, 8 mild asthmatic patients and 8 mild chronic obstructive pulmonary disease(COPD) patients aged 55 to 75 years, inclusive, will be randomized at a single center.

Study period

Estimated date of first subject enrolled

Estimated date of last subject completed

Phase of development

Clinical Pharmacology (I)

Objectives

The primary objective of the study is to:

- Assess the effect of AZD6140 on respiratory rate and minute ventilation

The secondary objectives of the study are to:

- Assess the effect of AZD6140 on other respiratory parameters;

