2.2 Secondary objective(s)

The secondary objectives of the study are to:

- Assess the effect of AZD6140 on other respiratory parameters;
- Evaluate the pharmacokinetic/pharmacodynamic (PK/PD) relationship between AZD6140/AR-C124910XX concentrations and respiratory parameters in healthy volunteers, mild asthma patients, and mild COPD patients;
- Compare respiratory parameters between the healthy volunteers, mild asthma patients, or COPD patients;
- Compare PK of AZD6140 and AR-C124910XX in healthy volunteers, mild asthma patients, or COPD patients.
- Examine the safety and tolerability of AZD6140 in healthy volunteers compared with mild asthma patients, or mild COPD patients.

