3. STUDY PLAN AND PROCEDURES

3.1 Overall study design

This will be a randomized, double blind, placebo-controlled, 3 cohort PK/PD, single center study to assess the effect of AZD6140 on respiratory parameters in healthy volunteers, mild asthmatic and COPD patients between 55 to 75 years of age.

Up to 12 men or women (non childbearing potential) will be randomized in each cohort to ensure the completion of at least 8 subjects within each cohort.

Cohort	Volunteer Type	Respiratory criteria	Number subjects
A	Healthy	N/A	8
B	Mild Asthmatic	FEV ₁ > 70%; no exacerbation in past 8 weeks; reversibility demonstrated within the past year (\geq 12% or 200 mL)	8
C	Mild COPD	FEV ₁ \geq 60%; no exacerbations in past 8 weeks; history of tobacco smoking > 10 pack years	8

On Study Day 1 of Period I, each subject will receive one of the following treatments according to the randomization schedule:

Treatment A: A single, oral dose of 450 mg AZD6140 (5 x 90 mg immediate release tablets) will be administered in the AM of Study Day 1; followed by a single, oral dose of 180 mg AZD6140 (2 x 90 mg immediate release tablet) in the PM (12 hours after the first dose); thereafter, 180 mg AZD6140 (2 x 90 mg immediate release tablet) will be administered bid (every 12 hours) on Study Days 2 and 3 and in the AM only on Study Day 4.

Treatment B: A single, oral dose of AZD6140 matching placebo (5 placebo tablets) will be administered in the AM of Study Day 1; followed by a single, oral dose of AZD6140 matching placebo (2 placebo tablets) in the PM (12 hours after the first dose); thereafter, AZD6140 matching placebo (2 placebo tablets) will be administered bid (every 12 hours) on Study Days 2 and 3 and in the AM only on Study Day 4.

At the end of Period I, all subjects will crossover to receive the alternate treatment following a 7 – 10 day washout period. During each treatment period, pharmacodynamic measurements and safety variables will be assessed. Blood samples will be collected for analysis of AZD6140 and its metabolite, AR-C124910XX.

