3.4.2 Doses and treatment regimens

Each subject will receive each of the following treatments in one of two treatment sequences (AB or BA) according to the randomization schedule:

Treatment A: A single, oral dose of 450 mg AZD6140 (5 x 90 mg immediate release tablets) will be administered in the AM of Study Day 1; followed by a single, oral dose of 180 mg AZD6140 (2 x 90 mg immediate release tablet) in the PM (12 hours after the first dose); thereafter, 180 mg AZD6140 (2 x 90 mg immediate release tablet) will be administered bid (every 12 hours) on Study Days 2 and 3 and in the AM only on Study Day 4.

Treatment B: A single, oral dose of AZD6140 matching placebo (5 placebo tablets) will be administered in the AM of Study Day 1; followed by a single, oral dose of AZD6140 matching placebo (2 placebo tablets) in the PM (12 hours after the first dose); thereafter, AZD6140 matching placebo (2 placebo tablets) will be administered bid (every 12 hours) on Study Days 2 and 3 and in the AM only on Study Day 4.

All doses given in each treatment will be administered with 240 mL of room temperature water while the subject is sitting in an upright or in a semi-recumbent position. Subjects must remain either sitting or semi-recumbent for at least 2 hours after each dose intake.

On Study Days 1 and 4 of each treatment, the subjects will receive the AM study medication following an overnight (10 hour) fast and will continue to fast for 4 hours post dose. The PM

dose on Study Days 1, 2 and 3 will be given either 1 hour before or 1 hour after food intake. On Study Day 2 and 3, breakfast will be served 1 hour after the AM study medication.

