6. PHARMACOKINETIC, PHARMACODYNAMIC, SAFETY, GENETIC AND STATISTICAL METHODOLOGY

6.1 Pharmacokinetic / pharmacodynamic evaluation

6.1.1 Calculation or derivation of pharmacokinetic variables

The pharmacokinetic analyses will be performed by Clinical Pharmacokinetics, Experimental Medicine, AstraZeneca, Wilmington, DE. To be followed by a description of each pharmacokinetic variable to be included in the analysis and the means by which each is calculated.

Plasma concentrations of AZD6140 and its metabolite AR-C124910XX will be listed and depicted graphically as a function of time relative to Day 1 dose for the 3 cohorts. Pharmacokinetic parameters listed below will be estimated by non-compartmental analysis.

Day 1: C_{max} , t_{max} , AUC_{0-12} of AZD6140 and AR-C124910XX, metabolite to parent C_{max} and AUC ratios

Day 4: C_{max} , t_{max} , AUC_{τ} , metabolite to parent C_{max} and AUC ratios of AZD6140 and AR-C124910XX and, AZD6140 steady state CL/F.

AZD6140 and AR-C124910XX C_{max} will be estimated as the highest measured concentration and t_{max} will be the time to maximum concentration within a dosing interval on Days 1 and 4. AUC_{0-12} and AUC_{τ} will be calculated using the linear trapezoidal method over the 12 hour dosing interval on Days 1 and 4, respectively. AZD6140 CL/F will be estimated as the ratio of AZD6140 dose and AUC_{τ} on Day 4. The ratio of AR-124910XX C_{max} to AZD6140 C_{max} ratio and, AR-124910XX AUC to AZD 6140 AUC ratio will be calculated on Days 1 and 4.

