6.4.3 Methods of statistical analyses

Statistical analysis will be carried out by Biostatistics at AstraZeneca, Wilmington, Delaware using SAS (version 8.2). Graphics to be included in the text or intended for use as supplemental figures and individual profile figures will be made using SAS or other software. Pharmacokinetic analysis will be carried out by, or under the guidance of, the Pharmacokinetic Section, Experimental Medicine, at AstraZeneca, Wilmington, Delaware.

No formal statistical analysis of the pharmacodynamic, pharmacokinetic or safety data will be done.

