6.4.3.3 Pharmacodynamic/Pharmacokinetic

Relationship between AZD6140 concentration and PD endpoints will be explored graphically. Representative plots include:

- Plots of individual numeric value from Modified Borg Scale and Bidirectional Dyspnea Index versus AZD6140 concentrations
- Plots of individual and mean respiratory rate, V_E , V_T , f , FVC, FEV₁ versus AZD6140 concentrations
- Plots of individual and mean PCO₂, PO₂ and pH versus AZD6140 concentrations

Regressions techniques may be utilized to provide estimates of slope, along with corresponding 95% confidence intervals, for the relationships above, if distributional assumptions underlying this analysis can be confirmed.

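### Comparing pharmacokinetics between cohorts is a stated secondary objective, but the protocol plans no between-cohort ratio and no measure of its uncertainty

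*Protocol*

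**What the plan says.** The secondary objectives (protocol synopsis and section 2.2) include: "Compare PK of AZD6140 and AR-C124910XX in healthy volunteers, mild asthma patients, or COPD patients".

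Three places set out how the pharmacokinetic data will be handled:

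- Section 6.1.1 derives Cmax, tmax and AUC on Days 1 and 4, the metabolite-to-parent ratios, and steady-state CL/F for the parent. Plasma concentrations "will be listed and depicted graphically as a function of time relative to Day 1 dose for the 3 cohorts".
- Section 6.4.3.2 states: "All pharmacokinetic parameters will be descriptively summarized by treatment and listed by individual at each scheduled time point for each of the cohorts". Concentrations are treated in the same way.
- Section 6.4.3 states: "No formal statistical analysis of the pharmacodynamic, pharmacokinetic or safety data will be done".

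The only intervals mentioned in the statistical section are optional ones for concentration-response slopes, in section 6.4.3.3: "Regressions techniques may be utilized to provide estimates of slope, along with corresponding 95% confidence intervals, for the relationships above".

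The synopsis plans "8 healthy volunteers, 8 mild asthmatic patients and 8 mild chronic obstructive pulmonary disease(COPD) patients". Section 3.1 allows up to 12 randomised per cohort "to ensure the completion of at least 8 subjects within each cohort". Section 6.4.4 says that the sample size rests on feasibility and not on a power calculation. Section 6.4.1 announces a statistical analysis plan, which is not at hand.

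**The concern.** The objective asks for a comparison, but the methods describe each cohort separately. Nothing in sections 6.1.1, 6.4.3 or 6.4.3.2 calls for a ratio or difference between cohorts, or for any statement of how precisely the data determine it.

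This matters because patients are included partly to see whether they are more sensitive than healthy volunteers (sections 1.2 and 3.2). If the respiratory response is larger in a patient cohort, higher exposure is one possible explanation. The cohorts are not randomised against each other, so equal exposure cannot be presumed. Means placed side by side make it easy to report that exposure was similar, without showing how large a difference the data leave open.

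**Working it through.** **Inputs**

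- Subjects per cohort: 8 planned (synopsis), with at least 8 completers intended (section 3.1). The upper bound is 12, although section 3.4.3 describes the four extra drug packages per cohort as back-up only.
- Type of comparison: every subject receives AZD6140 in one of the two periods (section 3.4.2), so each cohort contributes all its subjects. The contrast between cohorts is between-subject; the crossover does not sharpen it.
- Between-subject CV of exposure: not given in the protocol. Assumed here as 30%, 40%, 50% or 60%.

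The plan has no figure of its own to reproduce, since section 6.4.4 reports no calculation.

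**Formulas**, for a ratio of geometric means of two independent cohorts of n subjects each:

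- SD on the log scale: s = √ln(1 + CV²)
- Standard error of the log ratio: SE = s × √(2/n). For n = 8, √(2/8) = 0.5.
- 95% interval: estimate divided and multiplied by exp(t × SE), with t on 2n − 2 degrees of freedom. For n = 8 there are 14 degrees of freedom and t = 2.145.

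**Results, 8 against 8**

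| Assumed CV | s | SE | Factor | 95% interval if the observed ratio is 1.00 |
|---|---|---|---|---|
| 30% | 0.294 | 0.147 | 1.37 | 0.73 to 1.37 |
| 40% | 0.385 | 0.193 | 1.51 | 0.66 to 1.51 |
| 50% | 0.472 | 0.236 | 1.66 | 0.60 to 1.66 |
| 60% | 0.555 | 0.277 | 1.81 | 0.55 to 1.81 |

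The CV at which the factor reaches 1.5 follows by inversion: s = ln(1.5) / (2.145 × 0.5) = 0.4055 / 1.072 = 0.378, and CV = √(exp(0.378²) − 1) = 0.39. The threshold is therefore about 40%.

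**Sensitivity to the number of subjects.** With 12 against 12, the interval around 1.00 is 0.78 to 1.28 at 30% CV, 0.72 to 1.39 at 40%, 0.67 to 1.49 at 50% and 0.63 to 1.60 at 60%. The 1.5-fold threshold then moves to a CV of just over 50%.

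**Sensitivity to the model.** Pooling the variance over the three cohorts of 8 (21 degrees of freedom) gives factors of 1.36, 1.49, 1.63 and 1.78, which is little different.

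**CL/F.** Section 6.1.1 defines parent CL/F as dose over Day 4 AUCτ, and section 3.4.2 schedules the same Day 4 dose for all subjects. The cohort ratio of CL/F is then the reciprocal of the cohort ratio of AUCτ, so a separate interval adds nothing.

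**The case against.** The strongest reply is that this is an exploratory phase I study with feasibility-based numbers. Summaries, individual listings and plots of three cohorts are a legitimate descriptive comparison, and the choice of tabulated statistics commonly belongs in the analysis plan. Much of this stands. No hypothesis test or larger sample is needed, and the exact table layout can be left to the analysis plan. What remains is that the protocol itself sets both the objective and the method, and the method contains no between-cohort quantity.

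Four stronger readings are tempting but go beyond the documents:

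- **That section 6.4.3 bars any interval.** It excludes formal statistical analysis of pharmacodynamic and pharmacokinetic data, yet section 6.4.3.3 permits slopes with 95% confidence intervals on those same data. Estimation is therefore not clearly excluded. The sentence is ambiguous and needs clarifying, not deleting.
- **That 8 against 8 cannot exclude large differences.** This depends on a CV the protocol does not give. At 30% an interval centred on 1.00 ends at 1.37 and does exclude 1.5-fold.
- **That the cohort comparison of exposure is the only way to separate sensitivity from exposure.** Table 2 schedules concentrations and resting respiratory measures at the same times. The synopsis and section 6.4.3.3 plan concentration-response plots, by cohort, with optional slopes. Those address response at a given concentration more directly. The exposure ratio complements them by showing how far exposure itself could differ.
- **That summarising parameters by treatment and scheduled time point is an error.** The phrase suits concentrations better than parameters, but the time points can be read as Day 1 and Day 4. This is minor.

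No rule for concluding similar exposure appears in the protocol, so the misreading described above is a risk and not a planned step.

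**Conclusion.** The point holds as a modest one. The protocol names a between-cohort comparison of pharmacokinetics as a secondary objective and plans only per-cohort description, so the plan as written provides neither a ratio nor its uncertainty.

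How much this hides depends on the between-subject CV, which is assumed here, and on log-scale data with about 8 subjects per cohort. At 40% to 60%, an observed ratio near 1 would still be compatible with a true difference of about 1.5- to 1.8-fold. At 30% the open range shrinks to about 1.4-fold. The study can still compare its cohorts descriptively; it lacks the number that would state the comparison and its limits.

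**What to change.** 1. In section 6.4.3.2, add asthma/healthy and COPD/healthy geometric mean ratios with 95% intervals, computed on log-transformed values and presented as estimation without testing. Cover Day 1 Cmax and AUC(0-12) and Day 4 Cmax and AUCτ, for AZD6140 and AR-C124910XX. Parent CL/F needs no interval of its own.
2. In section 6.4.3, clarify that the exclusion of formal statistical analysis means no hypothesis tests. This also removes the tension with the slope intervals in section 6.4.3.3.
3. Require that any statement of similar exposure between cohorts quote the corresponding interval.

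If only description is wanted, the alternative is to reword the objective in the synopsis and section 2.2 so that it says so.

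The cost is one additional table and a more cautious conclusion. No further subjects, samples or visits are needed.

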6.4.3.3 Pharmacodynamic/Pharmacokinetic

Relationship between AZD6140 concentration and PD endpoints will be explored graphically. Representative plots include:

- Plots of individual numeric value from Modified Borg Scale and Bidirectional Dyspnea Index versus AZD6140 concentrations
- Plots of individual and mean respiratory rate, V_E , V_T , f , FVC, FEV₁ versus AZD6140 concentrations
- Plots of individual and mean PCO₂, PO₂ and pH versus AZD6140 concentrations

Regressions techniques may be utilized to provide estimates of slope, along with corresponding 95% confidence intervals, for the relationships above, if distributional assumptions underlying this analysis can be confirmed.

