1.2 Rationale

This study is to be conducted to evaluate the respiratory symptoms and physiological parameters that may be associated with the sensation of dyspnea in subjects receiving AZD6140. Dyspnea was reported in association with AZD6140 administration in DISPERSE, a phase IIa study in stable outpatients with documented atherosclerosis, but not healthy volunteers. One pre-clinical study in rats demonstrated an increase in respiratory rate at concentrations of AZD6140 that are clinically relevant. Non-clinical studies have demonstrated that, at relatively high concentrations, AZD6140 has an affinity for the adenosine transporter in erythrocytes. This is a potential mechanism for the observed effect. Adenosine administration has been associated with dyspnea, flushing, and chest discomfort. Dyspnea has also been observed clinically with dipyridamole, which inhibits the erythrocyte adenosine transporter. Respiratory symptoms invoked by adenosine are thought to be due to activation of arterial chemoreceptors. The target population of patients with ACS are likely to include those with asthma and COPD. Therefore healthy volunteers, as well as patients with mild asthma and COPD will be included to assess whether the sensitivity of patients with respiratory disease is greater than in healthy volunteers. The pharmacodynamic effect of AZD6140 on respiratory parameters will be assessed by cardiopulmonary exercise test, respiratory rate, minute ventilation, spirometry (FVC, FEV₁), modified Borg Scale¹, and Bidirectional Dyspnea Index². Pharmacokinetics of AZD6140 and its active metabolite AR-C124910XX will be assessed to correlate the PD effect on respiratory parameters with plasma concentrations of AZD6140 and AR-C124910XX.

A retrospective analysis of the polymorphisms of genes that are important to the absorption and disposition of, and response to AZD6140 may be performed. The genetic data from this study may be pooled with genetic results from other studies on AZD6140 to generate hypotheses to be tested in future studies. The results of the genetic analysis, if any, will not form part of the clinical study report.

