4. MEASUREMENT OF STUDY VARIABLES

The following study measurements will be obtained. The timing of these measurements is detailed in the study plan (Table 1). The following 'priority order' will be in effect when more than one assessment is required at a particular time point:

- Modified Borg Scale/Bidirectional Dyspnea Index
- Minute ventilation including respiratory rate
- Pulse oximetry
- ABG (will only be performed if a subject experiences an acute episode of dyspnea)
- Spirometry

- Blood pressure/heart rate
- ECG
- PK sample

Note: In order to collect PK sampling at the precise scheduled time, other assessments may be initiated prior to the time point to ensure that the PK sample is collected at the scheduled time. The exact time for PK and PD samples will be recorded in the CRF.

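### The PK/PD analysis omits the active metabolite named in the objective, and plans means and optional slopes for blood gases that exist only at dyspnea episodes

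*Protocol*

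**What the plan says.** **Analyte.** The secondary objective in Section 2.2 (repeated in the Synopsis) is to evaluate the PK/PD "relationship between AZD6140/AR-C124910XX concentrations and respiratory parameters in healthy volunteers, mild asthma patients, and mild COPD patients". Section 1.2 describes AR-C124910XX as the active metabolite and gives the reason for sampling both analytes: "to correlate the PD effect on respiratory parameters with plasma concentrations of AZD6140 and AR-C124910XX". Section 6.1.3 and the opening of Section 6.4.3.3 then read "Relationship between AZD6140 concentration and PD endpoints will be explored graphically". Each of the three bullets in Section 6.4.3.3 repeats AZD6140 as the only concentration axis, and so does the graphical plan in the Synopsis.

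**Blood gases.** The third bullet of Section 6.4.3.3 lists individual and mean PCO2, PO2 and pH against AZD6140 concentration. The paragraph after the bullets applies to all the listed relationships: "Regressions techniques may be utilized to provide estimates of slope, along with corresponding 95% confidence intervals", provided the distributional assumptions hold. Section 4 restricts the measurement: "ABG (will only be performed if a subject experiences an acute episode of dyspnea". Note h to Table 1 and Section 4.3.6 say the same.

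**Response scale.** The second bullet begins "Plots of individual and mean respiratory rate" and lists parameters by name. It mentions neither change from baseline nor the placebo period. Section 6.1.2 derives changes from baseline within each period, and Section 3.2 justifies the crossover by the wish to compare with placebo.

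**The concern.** The study was set up to explain dyspnea seen with AZD6140 in patients, and the PK/PD objective asks whether exposure to either analyte tracks the respiratory measures. An analysis confined to the parent cannot answer for the metabolite. Parent and metabolite rise and fall together over a dosing schedule, so a parent-only plot may also show a relation that belongs to the metabolite.

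The blood-gas issue is different in kind. Values exist only when the subject is already short of breath. If blood gases influence whether dyspnea occurs, sampling is conditioned on something downstream of the response, and the apparent relation with concentration is distorted. There is no scheduled baseline, no symptom-free value on either treatment, and no common time point at which a mean across subjects has a clear meaning.

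**Working it through.** The protocol gives no slope, SD or power figure for the PK/PD analysis, so there is no stated figure to reproduce. The check sets sections side by side and adds illustrative arithmetic.

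**1. Analyte coverage**

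| Place | AZD6140 | AR-C124910XX |
|---|---|---|
| Objective, 2.2 | yes | yes |
| Rationale, 1.2 | yes | yes |
| Assay, Table 5 (17 times per period) | yes | yes |
| PK derivation and summary, 6.1.1 and 6.4.3.2 | yes | yes |
| PK/PD derivation, 6.1.3 | yes | no |
| PK/PD analysis, 6.4.3.3 | yes | no |

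The data exist; only the PK/PD step drops the metabolite.

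**2. Could the parent be credited with a metabolite effect?** Simulation inputs from the protocol: Table 5 times, the 450/180 mg schedule, half-life 6 to 13 h, metabolite exposure about 35% of parent (Section 1.1). Assumed: slower metabolite formation, no parent effect, metabolite slope 3 per unit, 24 subjects, no time-of-day effect. The parent-metabolite correlation over the schedule was 0.90. The parent-only slope came out at 0.69 to 0.85 across four ways of fitting, although the true parent effect was 0. For scale, exact proportionality would give 3 × 0.35 = 1.05. Fitting placebo-matched differences did not remove it (0.71 to 0.79).

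**3. How many subjects would supply a blood gas?** Expected number = n × p; chance of none in a cohort of 8 = (1 − p)^8. The rates come from Section 3.2 and are assumed to carry over.

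- p = 0.20 (400 mg level in the earlier patient study): 8 × 0.20 = 1.6 per cohort, 24 × 0.20 = 4.8 in all; 0.80^8 = 0.168, a 17% chance of none.
- p from the 5 patients at that level with dyspnea in the first 3 days, assuming four equal AZD6140 arms: 163/4 = 40.75 and 5/40.75 = 0.123. Then 8 × 0.123 = 0.98 per cohort, with 0.877^8 = 0.35 for none.
- p for healthy volunteers, 1 report in about 200: 8 × 0.005 = 0.04, with 0.995^8 = 0.96 for none.

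Episodes during the exercise test are excepted from the episode procedures (Section 3.1.2), so they do not add to these counts.

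**4. Effect of sampling on the symptom.** Assumed: the blood-gas value falls by 2 per unit of concentration, residual SD 2, and dyspnea occurs at the lowest values plus noise of SD 1. With 2%, 5%, 10% and 20% of time points sampled, the slope among the sampled points was −0.60, −0.63, −0.71 and −0.76 instead of −2. The size and direction depend on the assumed trigger.

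**5. Other endpoints, if slopes are reported.** Assumed: between-subject SD 3, within-subject SD 1.5, true slope 1, time-of-day amplitude 0 to 2, between-subject slope SD 0 or 1; 8 or 24 subjects; 600 runs per setting.

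| Fit | Mean slope | 95% interval coverage |
|---|---|---|
| Active-period values, pooled, amplitude 0 | 0.94 to 1.09 | 58% to 61% |
| Same, amplitude 1 | 1.49 to 1.70 | 53% to 57% |
| Same, amplitude 2 | 2.10 to 2.24 | 42% to 55% |
| Matched differences, pooled, equal slopes | 0.97 to 1.02 | 93% to 96% |
| Matched differences, pooled, slope SD 1 | 0.96 to 1.02 | 77% to 85% |
| Matched differences, one slope per subject | 0.93 to 1.04 | 94% to 97% |

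With no time-of-day effect the slope is about unbiased and the fault lies in ignoring repeated measures. A separate null run (8 subjects, within-subject correlation 0.6, concentration CV about 40%) gave 66% coverage for the pooled fit and 96% once a subject intercept was added, without any placebo matching.

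**The case against.** The strongest reply is that Section 6.4.3.3 is descriptive. It makes graphs the main tool, calls its list representative and makes regression optional and conditional. Section 6.4.3 rules out formal analysis, and Section 6.4.1 defers detail to an SAP that was not available here. This stands against a stronger reading that a reader might infer: that the plan fits raw values, treats the readings within a subject as independent, and so must give wrong slopes and intervals. No section specifies that fit, Section 6.1.2 derives changes from baseline, and the Bidirectional Dyspnea Index is already a change score. The response scale and the handling of repeated measures are ordinary SAP content.

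Time confounding is also only partial, because the same clock hour follows different doses and meal conditions on different days. Matching to placebo is not a complete cure either: with an assumed subject-by-period SD of 0.5, 0.75 or 1.0 breaths/min, a pooled fit to the differences covered 87%, 80% and 73%.

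On the metabolite, it can be said that concentrations are measured and summarised and that a representative list does not forbid more plots. But the restriction to AZD6140 is in the lead sentences of both sections, not only in the list, so the mismatch with the objective remains. Its omission does not invalidate a parent slope as an association.

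On blood gases, Table 3 pairs each episode with a PK sample, so showing individual values against concentration is legitimate. That defends the individual plots, not the means or slopes.

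One might also object that scheduled pulse oximetry appears in no plot. It is not among the pharmacodynamic variables in the Synopsis, so its absence contradicts nothing.

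**Conclusion.** Two points hold on the protocol text alone. The PK/PD sections omit an analyte that the objective and rationale name, so the metabolite part of that objective is unmet if the plan is followed as written. The blood-gas means and optional slopes would rest on few, symptom-selected samples: about 1.6 of 8 subjects per cohort at a 20% rate, and fewer at the other rates in Section 3.2. They cannot be read as a concentration effect.

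The misattributed slope of 0.69 to 0.85 and the shrinkage from −2 to between −0.60 and −0.76 illustrate direction under assumed models; they are not predictions. With a correlation near 0.90, plotting both analytes meets the objective but will not by itself separate their effects.

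For the other endpoints the conclusion is conditional. If slopes are reported without allowing for repeated measures, intervals could be too narrow; if placebo values are not used, slopes could be biased by any time-of-day effect. The documents give no size for either.

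**What to change.** In Sections 6.1.3 and 6.4.3.3, with the Synopsis aligned:

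- Name both analytes, and repeat each concentration-response plot, and any slope, for AR-C124910XX. The list has 2 symptom scales and 6 respiratory measures, so this adds 8 endpoint relationships.
- Delete the mean plots and regression slopes for PCO2, PO2 and pH. List or plot individual values by episode, with treatment and the paired concentrations of both analytes.
- State that any slope for the scheduled endpoints will use the same subject's time-matched placebo values and allow for repeated measures, for example through subject-level intercepts and slopes or the mean of per-subject slopes. This sentence may sit in the SAP.

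The cost is wording, extra plots and some analysis time. All the data are already collected, and no study procedure changes.
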